### *Analysis of Safety and Tolerability of Omegaven®*

All primary safety and tolerability analyses will be based on descriptive statistics. In secondary analyses, we will also assess the statistical significance of differences. The period receiving Omegaven® will start 30 days after beginning PN with Omegaven® for the main analysis. Outcomes measured in the Omegaven® will be described for a period starting 30 days after baseline.

Primary outcomes measured will include whether the triene/tetraene ratio was ever  $> 0.2$  during the intervention period and whether the INR was ever  $> 2$ . Secondary outcomes measured will include platelets, prothrombin time (PT), partial thromboplastin time (PTT), and other components of the fatty acid profile. Analysis of all categorical outcomes will be based on proportions and of all continuous outcomes will be based on means or medians of the individual mean, maximum or minimum values, as appropriate, during the respective follow-up period. Comparisons between periods (pre and post-treatment) will be performed based on paired tests, parametric or non-parametric, as appropriate. We will also explore trends over time (e.g., decreasing for INR and increasing for pre-albumin) and estimate p-values via regression models using generalized estimating equations or random effects to account for within subject correlations. When describing outcomes over time, we will explore the effect of predictors of poor hepatic outcomes, such as use of antifungal agents (e.g., amphotericin) and antidiarrheal agents (e.g., loperamide), on potential spikes.

[name], Department of Surgery, Children's Hospital & Medical Center  
[name], Department of Surgery, Children's Hospital & Medical Center  
[name], Pediatric Research Office, Dept. of Pediatrics, UNMC  
[name], Department of Biostatistics, College of Public Health, UNMC

We will also evaluate nutritional outcomes including difference in weight-for- age Z-scores and height-for-age Z-scores from baseline to the moment in which the child starts enteral feeding and to the moment in which the child receives less than 10% of their calories from PN. Using linear regression, we will explore adjustment for baseline alternative predictors of interest. Trends over time in Z-scores will also be explored using regression with repeated measure methods.

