#### *Analysis of Efficacy of Omegaven®*

The primary outcome to gain preliminary evidence of efficacy will be based on the time from baseline to normalization of bilirubin level, i.e., first time point among three consecutive in which bilirubin is < 2 mg/dL. We do not anticipate that any subject will present a rebound on direct bilirubin after normalization. However, we will describe the cohort with respect to the frequency of rebounds in bilirubin levels.

Time to normalize direct bilirubin levels will be estimated using Kaplan-Meier curves. We will estimate hazard ratios and adjust for potential baseline confounders using Cox-proportional hazard models. For all survival analysis based on non-parametric or semi-parametric methods, we will attribute an infinite time to event for subjects who die or receive a liver transplant before bilirubin is normalized. Subjects who die before their bilirubin levels normalize (particularly due to liver failure) have in fact the worst outcome (infinite time to normalize bilirubin) and were not censored before reaching the endpoint of interest. Results of these analyses will be compared with results of analysis excluding subjects who die or are transplanted. Time to reach a total bilirubin of 1.2 will also be estimated using survival analysis methods. Analyses of this outcome will proceed as described for direct bilirubin.

We will also describe individual profiles over time (i.e., 2 months before baseline or birth until end of follow-up period) for all subjects using graphical methods. Trends in liver function markers over time will be explored using generalized linear models in which correlations of observations within subjects will be accounted using a generalized equations or random effects approach. We will perform these analyses including only subjects who did not die or undergo transplantation and including all subjects but assigning for subjects who died or underwent a transplant their worse possible outcome after they died or had the transplant. Using descriptive statistics, we will also explore the association between spikes in blood tests over time and predictors including transfusions of red blood cell products and blood stream infections.

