#### *Statistical Power and Sample Considerations*

The number of subjects included in the study will be based on a compassionate use protocol and not on study power considerations. The primary safety analysis will be descriptive and not based on statistical significance. However, in Table 4 we outline power to detect several differences in the frequency of adverse events, assuming 20, 25, or 30 patients, diverse proportion of subjects with adverse event in either treatment period and not with the adverse event in either treatment period and not with the adverse event in the other (proportion of discordant pairs), for a two-sided 5% significance level McNemar's tests.

For lower proportions of discordant pairs, we would generally attain close to 80% power in McNemar's test. Even for higher proportions of discordant pairs, assuming the high differences between before and after treatment that we expect to observe, e.g., 50% or more, 80% power can be attained in McNemar's test (Table 4).

Table 4—Power to detect varying differences in proportions before and after treatment with Omegaven® in a McNemar's test. All calculations based on an alpha significance level of 0.05

Difference between proportions	Proportion of discordant pairs	McNemar's Test		
		Sample Size		
		20	25	30
30%	40%	59%	72%	81%
	60%	44%	55%	63%
50%	60%	92%	97%	99%
	80%	79%	88%	93%
80%	85%	>99%	>99%	>99%
	95%	>99%	>99%	>99%

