#### **Safety Labs Schedule:**

Lab Name	Schedule*
Serum triglycerides	At baseline, weekly for 4 weeks, monthly thereafter
Coagulation labs	At baseline, weekly until direct bilirubin is < 2mg/dL, monthly thereafter
Fatty acid profile	At baseline, monthly thereafter

\*minimum requirements, may be performed more frequently for routine clinical care

If under the discretion of the principal investigator the patient is able to return home and receive Omegaven®, the patient is required to return to Children's Hospital & Medical Center every 2 months or other mutually agreed upon schedule for evaluation and follow up. The Principle Investigator also requires for arrangements to be made through the patient's home health care agency for the required weekly or monthly blood draws the patient will need while at home in order to remain on Omegaven®. The lab results then must be faxed to Children's Hospital & Medical Center in a timely manner. Additionally, measures will be taken to decrease the chance of administration errors when Omegaven® is given in the home. Families will be provided with a letter outlining strategies for reducing medication administration errors, such as independent double-checks.

Dose reduction will occur if there is evidence of lipid intolerance (serum triglycerides  $>$  200mg/dL) or evidence of bleeding. Growth indices include weight, length, and head circumference will also be monitored.

Other standard care laboratory results will be captured for the Omegaven® protocol. These are listed along with the standard schedule in Table 3.

The frequency of laboratory monitoring may be reduced to monthly or as clinically necessary, for patients who have been on a stable regimen of Omegaven® for a minimum of 4 months and whose serum bilirubin and hepatic enzymes have normalized.

The study team will round on all inpatients receiving Omegaven® therapy. A complete comprehensive case review for all inpatients receiving Omegaven® therapy under the compassionate-use protocol and any outpatients issues will be discussed among [name], [name], and the study coordinator. All pertinent medical, nutritional, and psychosocial outpatient information will be reviewed during these case reviews.

[name], Department of Surgery, Children's Hospital & Medical Center  
[name], Department of Surgery, Children's Hospital & Medical Center  
[name], Pediatric Research Office, Dept. of Pediatrics, UNMC  

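### The exploratory trend models should name a random-intercept-and-slope mixed model, because few children and bilirubin-driven lab timing can distort GEE or random-intercept results

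*Protocol*

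**What the plan says.** In the Protocol, Analysis of Safety and Tolerability, the primary layer has no test: "All primary safety and tolerability analyses will be based on descriptive statistics". Trends come after that: "We will also explore trends over time", with INR and pre-albumin as examples, and the plan is to "estimate p-values via regression models using generalized estimating equations or random effects to account for within subject correlations".

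Analysis of Efficacy does the same for liver markers: "Trends in liver function markers over time will be explored using generalized linear models", where "correlations of observations within subjects will be accounted using a generalized equations or random effects approach". Neither section names a working correlation, a type of standard error or the random-effects terms.

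The timing of observations depends on the child's own bilirubin in three ways.

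- **Draw frequency.** Under the Safety Labs Schedule, coagulation labs are due "At baseline, weekly until direct bilirubin is < 2mg/dL, monthly thereafter". The Reversal Study Lab Schedule makes the same switch for AST, GGT and PT/PTT/INR, and for the outpatient PN profile. Table 3 suggests it for most labs.
- **Later thinning.** Monitoring may be cut back further in children whose markers have normalized.
- **End of the safety window.** Section D closes it two months after the first direct bilirubin below 2 mg/dL.

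Not every lab follows the switch. The inpatient PN profile stays weekly below 2 mg/dL. The required minimum for triglycerides and fatty acids runs by calendar time only, although the Reversal schedule lists the lipid and fatty acid panels with the switch.

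On numbers, "The number of subjects included in the study will be based on a compassionate use protocol and not on study power considerations". Table 4 is computed "assuming 20, 25, or 30 patients". Treatment lasts until the child is weaned from PN, so follow-up differs between children.

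**The concern.** The text treats GEE and random effects as equivalent ways to handle within-child correlation. In this design they can differ for two reasons.

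1. The ordinary GEE sandwich standard error relies on many clusters. With 20 to 30 children of unequal follow-up it tends to be too small, and so are the p-values.
2. GEE needs observation times unrelated to earlier outcomes. Here a child whose bilirubin stays high gives about 52/12 = 4.3 draws for each one from a child on monthly draws, and also stays longer in the safety window. Slow responders therefore get more weight in the average slope. A likelihood model that lets each child have its own slope can allow for timing that depends on observed values. A model that omits the random slope does not.

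At stake are the exploratory trend p-values for INR, pre-albumin and similar markers, and the estimated rate of decline in bilirubin and liver enzymes that supports the second part of hypothesis 2.1.

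**Working it through.** The protocol gives no figure for the trend analysis that could be reproduced. Table 4 concerns McNemar's test and is used here only for the numbers of children.

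**Inputs from the protocol:** 20, 25 or 30 children; two-sided 5%; weekly draws until direct bilirubin is below 2 mg/dL, then monthly; safety window from day 30 to two months after the first value below 2.

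**Assumed, not in the protocol:** between-child slope SD 0.1 per month, intercept SD 0.3, residual SD 0.2; follow-up uniform over 8-52 weeks, or skewed (lognormal, median 20 weeks, range 8-104); bilirubin falling log-linearly from about 5 mg/dL; correlation of marker with bilirubin from 0 to 0.9; in the slope runs, every value follows the weekly/monthly switch.

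**Model.** Y_ij = a_i + b_i·t_ij + e_ij, with mean slope β = E(b_i). GEE solves β̂ = (Σ X_i′V_i⁻¹X_i)⁻¹ Σ X_i′V_i⁻¹Y_i and rejects when |β̂ / sandwich SE| > 1.96.

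**Step 1. P-values with true slope 0 and weekly visits.** Rejection rate (%) of uncorrected GEE at nominal 5%:

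| Follow-up | Working correlation | 20 | 25 | 30 |
|---|---|---|---|---|
| Equal | – | 7.4 | 6.5 | 6.2 |
| Uniform 8-52 weeks | Independence | 13.2 | 9.7 | 11.1 |
| Uniform 8-52 weeks | Exchangeable | 11.2 | 9.1 | 9.4 |
| Skewed | Independence | 40.5 | – | 32.9 |
| Skewed | Exchangeable | 32.3 | – | 26.0 |

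Monte Carlo error is about 0.8 to 1.3 points. A further simulation with 25 children put the rate at about 9-14%. With the Mancl-DeRouen correction and a t reference (children minus 2 degrees of freedom), the size is 3.9-4.5% (equal), 4.7-7.7% (uniform) and 11-13% (skewed).

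**Step 2. Slope bias by correlation with bilirubin** (25 children, true slope 0, weekly/monthly rule, per month):

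| Correlation | GEE independence | GEE exchangeable |
|---|---|---|
| 0 | -0.003 | -0.002 |
| 0.3 | +0.016 | +0.009 |
| 0.6 | +0.028 | +0.017 |
| 0.9 | +0.046 | +0.028 |

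With all draws weekly, or all monthly, the bias at correlation 0.6 is about 0. Over full follow-up, then, the schedule is the cause.

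**Step 3. Comparison of models** (25 children, 150 runs; marker correlation 0.6). Bias per month, with rejection of the true value at 1.96 in brackets:

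| Data | GEE independence | GEE exchangeable | Random intercept only | Random intercept and slope |
|---|---|---|---|---|
| Marker, true 0, weekly/monthly | +0.027 (25%) | +0.016 (17%) | +0.016 (71%) | -0.001 (5%) |
| Marker, true 0, all weekly | -0.003 (13%) | -0.002 (11%) | -0.002 (77%) | 0.000 (9%) |
| Marker, true 0, weekly/monthly, safety window | +0.090 (67%) | +0.055 (53%) | +0.056 (90%) | +0.0055 (8%) |
| Log bilirubin, true -0.25, weekly/monthly | +0.105 (35%) | +0.064 (25%) | +0.064 (78%) | +0.001 (7%) |

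Monte Carlo error on these percentages is 2-4 points.

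**Step 4. Attenuation for log bilirubin** = bias / |true slope|. Independence: 0.105/0.25 = 42%, a fitted slope of about -0.145. Exchangeable or random intercept only: 0.064/0.25 = 26%, about -0.186.

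**Step 5. Cause inside the safety window.** The independence bias is +0.090 with the weekly/monthly rule and +0.091 with weekly visits throughout. There the bilirubin-triggered end of follow-up produces the bias, not the spacing of draws.

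**The case against.** The strongest reply is that the protocol states no wrong formula. It fixes neither the standard error nor the working correlation, and small-sample corrections usually belong in a SAP, which is not shown here. A suitable random-effects model is already allowed. Primary safety is descriptive, primary efficacy is time to normalization by Kaplan-Meier and Cox, and the trends are only explored. The number of children is not fixed, and follow-up and variances are assumed. All of this stands, and it limits the weight of the point. What remains is that the protocol itself sets the pair of methods, the lab schedules and the end of the window, and these fit together badly.

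A reader might infer more than the document supports:

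- **That GEE will give p-values that are too small.** That describes the uncorrected default. With equal follow-up the excess is slight.
- **That deleting GEE is the cure.** A random-intercept-only model also counts as random effects, has the same slope bias as exchangeable GEE, and rejects a true null in about 71% of runs. The random slope is what matters.
- **That every trend is biased.** With no correlation to bilirubin there is no slope bias, the protocol gives no such correlations, and some labs do not follow the switch. If bilirubin is part of the PN profile, whose content the protocol does not define, inpatient values stay weekly and the log-bilirubin figure is at the high end.
- **That benefit would be overstated.** For log bilirubin the bias pulls the decline towards zero. For a marker positively correlated with bilirubin and truly flat, it produces a false rise.
- **That the method will be chosen after seeing both results.** A SAP could settle this, so it cannot be concluded from the protocol.

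**Conclusion.** The point holds in a limited form and is minor. Under moderately unequal follow-up, uncorrected GEE with 20 to 30 children rejects a true null in about 9-14% of tests instead of 5%. The rate is 6-7% if follow-up is equal and 26-41% in the skewed case tried. For bilirubin and markers that move with it, GEE or a random-intercept-only model can give biased slopes, roughly 25-40% attenuation for log bilirubin at -0.25 per month if all draws follow the switch. The weekly/monthly rule is the cause over full follow-up; within the safety window it is mainly the bilirubin-triggered end. A random intercept-and-slope model is close to unbiased in every setting tried.

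The sizes rest on the assumed follow-up, variances and linear trends. The simulations did not include the worst-possible values that Analysis of Efficacy assigns after death or transplant. The primary safety and efficacy results are not affected.

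**What to change.** In Analysis of Safety and Tolerability and in Analysis of Efficacy:

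- Name as the main trend model a linear mixed model with random intercept and random slope for time, fitted by REML with small-sample degrees of freedom such as Kenward-Roger.
- Use the log scale only for positive, skewed markers, not for Z-scores or age-standardized values such as pre-albumin.
- Fit it to all observations collected on treatment instead of cutting at the bilirubin-triggered end of the safety window, or report both.
- If GEE is kept, make it a sensitivity analysis with a small-sample corrected variance and a t reference. Under strongly skewed follow-up even that was not fully adequate (11-13%).

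The cost is about one sentence in each section, with no change to data collection. Some p-values will become less favourable.

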#### Hypothesis for Aim 1:

1.1 – After starting Omegaven® on PN, the rate of fatty acid deficiencies and imbalances will be as low as before Omegaven®. Also, the rate of triglyceride events > 400 mg/dL with Omegaven® will be similar to that seen with PN administered with soy oil IFE (conventional emulsion, i.e., Intralipid®).

1.2 – PN containing Omegaven® will be safe for patients with respect to the risk of unexpected bleeding, coagulopathies, and other adverse events.

[name], Department of Surgery, Children's Hospital & Medical Center  
[name], Department of Surgery, Children's Hospital & Medical Center  
[name], Pediatric Research Office, Dept. of Pediatrics, UNMC  
[name], Department of Biostatistics, College of Public Health, UNMC

1.3 – PN containing Omegaven® will promote more short-term growth and development than conventional fat emulsions.

2. To determine if established PN associated liver disease can be reversed or its progression halted by using a parenteral fat emulsion prepared from fish oil as measured by normalization of serum levels of hepatic enzymes and bilirubin.

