**Inclusion Criteria:**

1. Patients will be PN dependent (unable to meet nutritional needs solely by enteral nutrition) and are expected to require PN for at least another 30 days.
2. Patients considered eligible for study participation must have parenteral nutrition associated liver disease (PNALD) as defined as a direct bilirubin of  $\geq 2$  mg/dl on at least the last two consecutive measures or by histology and/or currently on Omegaven through another protocol and unable to remain on that protocol due to transfer to our institution. Other causes of liver disease should be excluded. A liver biopsy is not necessary for treatment.
3. The patient must have utilized standard therapies to prevent the progression of his/her liver disease including surgical treatment, cyclic PN, avoiding overfeeding, reduction/removal of copper and manganese from PN, advancement of enteral feeding, and the use of ursodiol (i.e., Actigall®).
4. Patients ages birth up to and including 18 years of age.

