### *Analysis of Baseline Characteristics*

For statistical purposes, baseline values will be defined as the last measurement before starting to administer Omegaven®. Descriptive statistics for all baseline relevant risk factors will be summarized using counts and percentages for categorical variables and means (and standard deviations) or medians (and interquartile ranges), when appropriate for continuous variables.

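### Two growth summaries end at feeding milestones that may precede baseline or are reached only by near-weaned children; the repeated-measures Z-score model should be the main growth analysis

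*Protocol*

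**What the plan says.** The growth outcome is defined in the section Analysis of Safety and Tolerability of Omegaven®. It is the difference in weight-for-age and height-for-age Z-scores over two intervals. One runs "from baseline to the moment in which the child starts enteral feeding", the other to "the moment in which the child receives less than 10% of their calories from PN". Linear regression is to explore adjustment for baseline predictors. The paragraph then adds: "Trends over time in Z-scores will also be explored using regression with repeated measure methods".

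Analysis of Baseline Characteristics fixes the starting point: "baseline values will be defined as the last measurement before starting to administer Omegaven".

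Inclusion criterion 1 requires only that enteral nutrition alone does not meet the child's needs. Inclusion criterion 3 requires prior use of standard therapies, a list that includes "reduction/removal of copper and manganese from PN, advancement of enteral feeding, and the use of ursodiol".

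Hypothesis 1.3, which the growth outcome serves, is comparative: "PN containing Omegaven® will promote more short-term growth and development than conventional fat emulsions".

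**The concern.** Each milestone fails as the end of a change score, for a different reason.

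The start of enteral feeding can lie before baseline. For a child who enters the study already taking some feed, there is no interval from baseline to that event, and the protocol gives no rule for the case.

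The fall below 10% of calories from PN is itself a favourable outcome after baseline. Averaging growth over the children who reach it conditions on their having done well. The interval also lasts as long as each child takes to get there, although the hypothesis is about short-term growth.

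At stake is the reading of the growth result. A favourable mean at the second milestone could reflect which children contribute rather than how treated children grow, and the first summary may rest on an unplanned subset.

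**Working it through.** The protocol gives no growth figure, so there is none to reproduce. The check sets its sections side by side and then illustrates the possible size of the selection effect.

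**First milestone: start of enteral feeding**

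1. Baseline is the last measurement before Omegaven® (Analysis of Baseline Characteristics).
2. Partial enteral feeding is compatible with entry (inclusion criterion 1).
3. Prior advancement of enteral feeding is among the therapies to have been used (inclusion criterion 3). Feeding can be advanced only once it has begun.
4. For a child in that position the milestone precedes baseline, and the change is undefined or negative in time.
5. Not every child need be in that position. Details of Omegaven® Administration foresees children who do not tolerate enteral feeds. For a child with no enteral intake at entry the milestone works as intended. The documents do not give the split.

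**Second milestone: less than 10% of calories from PN**

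1. Omegaven® continues until the child is weaned from PN (Duration of Therapy), so the interval varies with the child's course.
2. Transplantation, withdrawal on toxicity grounds and loss to follow-up all end participation (withdrawal list under Adverse Event Criteria and Reporting Procedures). These children, those who die and those who stay PN dependent may have no value.
3. The planned linear regression adjusts for baseline predictors. It supplies no value for a child who never reaches the milestone and does not equalise the intervals.
4. For bilirubin, Analysis of Efficacy of Omegaven® gives explicit rules for death and transplant. The growth paragraph has none.

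**Illustrative size at the second milestone**

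Assume that Z-score change and propensity to wean are bivariate normal with correlation rho, that a fraction f of children reach the milestone, and that the true mean change in all children is 0. The mean among those who reach it is then off by

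bias (in SDs of the Z-score change) = rho × phi(c) / f, with c = z(1 − f).

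Both f and rho are assumptions. The sample sizes of 20, 25 and 30 come from Table 4, which concerns adverse events and not growth.

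| f | c | phi(c) | phi(c)/f | rho = 0 | rho = 0.3 | rho = 0.5 | Contributors of 20 / 25 / 30 |
|---|---|---|---|---|---|---|---|
| 0.4 | 0.253 | 0.386 | 0.966 | 0 | 0.290 | 0.483 | 8 / 10 / 12 |
| 0.6 | −0.253 | 0.386 | 0.644 | 0 | 0.193 | 0.322 | 12 / 15 / 18 |
| 0.8 | −0.842 | 0.280 | 0.350 | 0 | 0.105 | 0.175 | 16 / 20 / 24 |

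The bias runs from 0 to about 0.5 SD over this grid. It is zero if growth is unrelated to weaning.

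**The case against.** The strongest reply is that the same paragraph already plans repeated-measures regression of Z-scores over time. That analysis needs neither milestone and can use measurements from every treated child, including those who never wean. A reader might infer from the two milestones that growth cannot be studied here without bias. The documents do not support that, because only two of the planned growth summaries are affected. It remains true that the sound analysis is the one the protocol merely explores.

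A reader might also infer that the first milestone is unusable for most children. The protocol does not say how many are enterally fed at entry, and it foresees some who cannot be. What stands is that no rule covers a child already fed.

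A third reply is that Z-scores are age-standardised, so a child tracking the reference has an expected change of zero over any interval. That removes ordinary growth with age. It does not remove the effect of interval length on a child who is gaining or losing ground against the reference.

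Finally, growth is ancillary. The safety analysis section names the triene/tetraene ratio and INR as primary outcomes, and describing growth up to near-weaning is reasonable under a treatment given until weaning. Some handling rules could also sit in an analysis plan not shown here. This limits the importance of the point, but the two end points are fixed in the protocol itself.

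**Conclusion.** The point holds for the two milestone-based change scores. The first is undefined for any child already partly enterally fed at baseline. The second describes only children who come close to weaning, over unequal intervals. Its bias cannot be computed from the documents. The illustrative 0 to about 0.5 SD rests on an assumed correlation of 0 to 0.5, on 40% to 80% of children reaching the milestone, and on a normal model.

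A reader might also think that better time points would let the study answer hypothesis 1.3. They would not. The hypothesis says Omegaven® "will promote more short-term growth and development than conventional fat emulsions", but the growth paragraph names no conventional-emulsion comparator, so neither the milestones nor fixed times can show superiority.

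This is a flaw in a supporting outcome that should be corrected and is cheap to correct. It does not touch the primary safety or efficacy analyses.

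**What to change.** 1. Make the repeated-measures model of weight-for-age and height-for-age Z-scores on time since baseline the main growth analysis, using all available measurements in all treated children. State that it uses data from baseline onward, because the Outcome/Endpoints section otherwise starts the safety window 30 days later.
2. Report estimates at fixed times that follow-up supports, for example 1 and 3 months, and 6 months where observed. A 6-month value is not secured for every child: entry requires only 30 further days of expected PN, and follow-up after stopping is a minimum of 2 months.
3. Report change at the two feeding milestones only as a description of the children who reach them after baseline, with the number who do. Count separately those already enterally fed at baseline and those who never fall below 10% of calories from PN.
4. State the growth conclusion as within-patient change and not as superiority under hypothesis 1.3.

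The cost is mainly wording and slightly more analysis work. The Data and Safety Monitoring Plan already has weight and length monitored. Table 3 schedules weight but gives no frequency for length, so it should be confirmed that length will be available near the chosen times. Later time points will have missing values for early weaners and withdrawn children. That loss may be related to outcome, so the number observed should be shown at each time.
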